6.4.4. Description of the assessments

The following assessments are performed during the study, at different timepoints according to Table 1.

Medical History with Demographics

Relevant cancer medical history and demographic information will be collected at the Baseline visit and reported on the applicable eCRFs.

Physical Examination

Complete physical examination includes, at a minimum, assessments of the skin, lymph nodes, respiratory system, abdomen, cardiovascular system, musculoskeletal system, genitourinary system, ear/nose/throat, measurement of height (in cm) and weight (in Kg).

Karnofsky Performance Scale

The Karnofsky Performance Scale Index classifies patients as to their functional impairment. This can be used to compare effectiveness of different therapies and to assess the prognosis in individual patients.

Functional status is assessed by the physician. The KPS ranges from 100 to 0, where 100 is “perfect” health and 0 is death. The lower the Karnofsky score, the worse the survival prognosis for most serious illnesses.

Not applicable for subjects with benign bone tumors.

PI Assessment of local tumor control

After procedure and during the follow-up, the PI can decide to assess the local control

Concomitant pain medications

All over-the-counter, prescription medication and/or herbal supplements used for palliative purposes are recorded on CRFs.

The specific concomitant medications listed below should be documented as concomitant medications and will be updated at each visit:

- Osteoporosis medication(s): Antiresorptive medications (e.g., bisphosphonates, parathyroid hormone (PTH), calcitonin), calcium, and vitamin D.
- Steroid(s): any steroid use, including steroid inhalers
- Oral narcotics in the last 24 hours. This information will be converted to oral morphine equivalent dose (OMED) (including transdermal patches)

Response rate at 3 months post RF ablation is defined in Table 6-1. Complete Response (CR) and Partial Response (PR) will be considered as treatment response.

Pain Progression (PP) and Indeterminate Response (IR) will be considered as treatment non-response.

Treatment Response	Complete Response (CR)	A worst pain score of 0 with no concomitant increase in daily oral morphine equivalent dose (OMED) within the last 24 hours.
	Partial Response (PR)	Pain reduction of 2 or more on a scale of 0-10 without increase in OMED, or OMED reduction of 25% in the last 24 hours or more from baseline without an increase in pain.
Treatment Non-response	Pain Progression (PP)	Increase in pain score of 2 or more above baseline worst pain score with stable OMED, or an increase of 25% or more in OMED within the last 24 hours compared with baseline with the worst pain score stable or 1 point above baseline.
	Indeterminate Response (IR)	Any response that is not captured by the complete response, partial response, or pain progression definitions.

Table 4 – Pain Response Table

Brief Pain Inventory (BPI)

The Brief Pain Inventory short form is a 9-question self-administered questionnaire used to evaluate the severity of a patient's pain and the impact of this pain on the patient's daily functioning. The patient is asked to rate their worst, least, average, and current pain intensity, list current treatments and their perceived effectiveness, and rate the degree to which pain interferes with general activity, mood, walking ability, normal work, relations with other people, sleep, and enjoyment of life. Each patient is instructed to rate their pain by circling the one number that best describes their pain at its worst in the last 24 hours on a 11-point scale (no pain = 0, pain as bad as you can imagine = 10).

The worst pain question in the BPI will be used to evaluate the pain severity:

The BPI pain interference, as defined in question 9, is typically scored as the mean of the seven interference items (general activity, mood, walking ability, normal work, relations with other people, sleeping, and enjoyment of life). The mean can be used if more than 50% or 4/7 of the total items has been completed.

The general pain question (Question #1), pain map (Question #2) and the medication question (Question #7) will not be used in this study. The removal of these questions does not affect the validity of the questionnaire and was approved by the BPI author Charles S. Cleeland, PHD

The BPI can be completed by the subject, by in-person interview or by phone interview by the Principal Investigator or qualified (delegated) designee.

European Quality of Life - Five Dimensions (EQ-5D-5L)

The European Quality of Life – Five Dimensions (EQ-5D), version 5L, is a standardized measure of health status developed by the EuroQol Group and a widely used validated tool to determine health-related quality of

life. The EQ-5D-5L consists of two sections, the descriptive system and the EQ visual analogue scale (EQ VAS).

The EQ-5D descriptive system consists of 5 dimensions: mobility, self-care, usual activities, pain/discomfort, and anxiety/depression. Each dimension has 5 levels of severity: no problems, slight problems, moderate problems, severe problems and extreme problems. The subjects are asked to indicate their health status by selecting the most appropriate statement in each of the 5 dimensions.

The EQ VAS records the respondent's self-rated health on a 20 cm vertical, visual analogue scale with endpoints labelled as 'the best health you can imagine' and 'the worst health you can imagine'. This information can be used as a quantitative measure of health as judged by the individual respondents.

The EQ-5D can be completed by the subject, in-person interview, or by phone interview by the Principal Investigator or qualified (delegated) designee.

Adverse Events Assessment

Any adverse event meeting the definition of device, therapy and/or procedure related, as well as all device deficiencies that occur from enrollment through subject discontinuation from the study will be collected.

All device, therapy and/or procedure-related adverse events will be collected for this study from enrollment to the end of the study, including events related to:

- The device components and/or procedure (Bone Access Kit, Probe, generator, etc.)
- Surgery or anesthesia regarding the initial or repeat procedure

Any adverse event due to the device, detected during the ablation procedure and/or during follow-up, will be recorded and evaluated through a dedicated case report form. The case report form will include at least the following information: date of the event, diagnosis or description of the event, severity assessment, treatment, outcome and date of resolution. The investigator is responsible for the detailed recording of the adverse event through the dedicated case report form and for the communication of the adverse event to the Sponsor.

The clinical course of each adverse event will be followed by the physician until resolution or until the subject's participation in the study is discontinued.

Deviations

Protocol deviations are digressions from the written protocol defined as an event where the clinical investigator or site personnel did not conduct protocol-required procedures according to the study protocol. Protocol deviations are to be pre approved by Axon study personnel and the IRB/EC (as required) unless the deviation is necessary to protect the health, safety, or welfare of a subject in an emergency situation. The investigator or delegated site personnel should immediately contact the designated Axon study personnel to discuss the impact of the potential deviation; prior approval of deviations should be documented. Prior approval is generally not required if the deviation is due to an emergency circumstance or an unforeseen circumstance that is beyond the investigator's control; however, these deviations should be reported to Axon and the IRB/EC (as required) after site personnel become aware of the deviation. All protocol deviations must be reported on the Protocol Deviation eCRF after the site's awareness of the deviation.

The sponsor may choose to terminate the study at a site for failure to follow the written protocol and investigator agreement.

Usability Assessment

At the end of the procedure the Investigator will fill-in a SPINERY device usability Case Report Form.

Tumoral lesion dimension

Subjects will be exposed to a small amount of radiation that they will receive during the study. The amount of this radiation cannot be determined in advance. For example, during the initial procedure, fluoroscopy or CT may be used according to standard of care at the site or an Investigator may order pre-operative or post-operative x-ray films or CT scans to assess the dimension of lesions/tumors. These images are routinely performed according to the standard of care; therefore, no additional radiation risk is associated with participation in this clinical study.

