5. ENDPOINTS

5.1. Primary Endpoints

The primary endpoints of the study are:

- Change of Worst Pain Score expressed as average reduction of 2 BPI (Brief Pain Inventory) scores: Thoracic/Lumbar/ Peri-acetabulum/Iliac Crest/Sacrum RF Ablation [Time Frame: Baseline vs. 3 months];

Change in pain will be calculated as:

$$\mu c = \text{worst-pain 3-month} - \text{worst-pain baseline}$$

A negative average value for change in pain represents a lowering of the subject's pain score (an improvement, or reduction in pain) and a positive value represents an increase in the subject's pain score (a worsening or increase in pain)

Worst pain score at the target treatment site will be collected from the BPI in the past 24 hours.

- Completion (%) of the ablation procedure without device-related adverse events including in particular nerve injury [Timeframe: Post-procedure, 3 months].

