6.3.2. Exclusion criteria

Participants are excluded from the study if *any* of the following criteria apply:

12. Patients implanted with heart pacemaker or other implanted electronic device;
13. Patients with previous mechanical bone stabilization in the vertebral body to be treated;
14. Use of SPINERY RF device in vertebral body levels C1-C7;
15. Multiple myeloma, solitary plasmacytoma, or primary malignant lesions in the index vertebra or bone;
16. Active or incompletely treated local infection at the planned treatment site(s) and/or systemic infection;
17. Planned treatment site(s) accompanied by objective evidence of secondary radiculopathy or neurologic compromise;
18. Planned treatment site(s) associated with spinal cord compression or canal compromise requiring decompression;
19. Fractures due to prostatic cancer or other osteoblastic metastases to the spine. Metastatic lesions originating in the prostate that are osteolytic or of mixed origin are eligible for the study;
20. Pregnancy, breastfeeding, or plan to become pregnant during the study duration;
21. Concurrent participation in another clinical study that may add additional safety risks and/or confound study results;
22. Any condition that would interfere with the subject's ability to comply with study instructions or might confound the study interpretation.

Exclusion criteria have been identified thanks to literature review concerning RF ablation contraindications¹:

- Criterion nr. 9 originates from the possibility of interferences between SPINERY and the implanted electronic device, which might be damaged by RF emission
- Criteria nr. 10-12-13-14-15-16 specify pathologies and conditions, which might confound study results interpretation
- Criterion nr. 11 originates from the incompatibility of vertebral bodies C1-C7 with SPINERY procedure in terms of shape and limited dimensions
- Criteria nr. 17-18 have been included for ethical reasons and to guarantee subjects' protection
- Criterion nr. 19 refers in general to subject's conditions which, according to physician's assessment, might not allow to comply with study procedures and/or might confound results interpretation

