6.4.3. Schedule of visits

Following signature of the informed consent, participants are enrolled in the study and perform the following study phases, as detailed in Table 1.

Enrollment and baseline visit. The eligibility criteria required by the protocol for participant's enrolment are assessed and evaluated and a comprehensive visit is performed to collect baseline parameters.

SPINERY Procedure. Patients are treated with RF ablation using SPINERY device. The use of bipolar or monopolar cooled needles or their combination is at physicians' discretion. More information is available in the instruction for use provided to each site.

Follow-up. Patients are followed-up within 24 hours from the RF ablation procedure, before the hospital discharge, and then after 1 month, 3 months and 12 months from the procedure.

	Enrollment Baseline	SPINERY procedure (Day 0) ²	Post- Procedure (within 24 hours)	1 month Follow-up (± 7 days)	3 Months Follow-up (±10 days)	12 Months Follow-up (±30days)
Informed Consent Form ¹	X					
Inclusion/Exclusion Criteria	X					
Medical History with Demographics	X					
Physical Examination	X		X		X	
Karnofsky Performance Scale	X					
PI assessment of local tumor control (optional)		X		X	X	X
Concomitant pain medications	X	X	X	X	X	X
BPI (Short Form) – includes worst pain score in the past 24 hours	X			X	X	X
EQ-5D-5L ³	X			X	X	X
Adverse Events Assessment	X	X	X	X	X	X
Deviations	X	X	X	X	X	X
Usability Assessment		X				
Tumoral lesion compatibility (clinical estimate)	X	X				
1) Informed consent must be obtained prior to performing any study-specific procedures. 2) Baseline Visit, Enrollment Visit and procedure can occur on the same day. 3) EQ-5D-5L is a standardized instrument for measuring generic health status						

Table 3 - Schedule of Visits

The attendance of subject to follow-up visits will be promoted by agreeing in advance on the schedule of visits with each subject. In addition, each subject will be contacted by phone a few days before the scheduled follow-up visit by the center to remember the need and the importance of attending the forthcoming control visit.

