8.2.3. Specific Adverse Device Effect (ADE)

The following ADE should be carefully assessed as they are recognized as possible ADE for SPINERY based on the state of the art of other medical devices:

- Carbonization
- Post-operative pain
- Limited/uncomplete treatment due to anatomical peculiarities
- Damage to surrounding tissue through iatrogenic injury
- Nerve injury including thermal injury, puncture of spinal cord or nerve roots potentially resulting in radiculopathy, paresis, and paralysis
- Pulmonary embolism
- Hemothorax or pneumothorax
- Infection
- Unintended puncture
- Hemorrhage
- Hematoma

Unanticipated adverse device effects can occur. If they do occur, they will be handled as discussed in paragraph 8.1.3.

Aside from the risks listed above, there are no known gender-specific risks associated with the use of the SPINERY device. Minimization of the risks will be accomplished by selection of patients who are appropriate candidates for this device and by careful selection of Investigators and centers that have appropriate experience with this type of procedure. Also, intervention techniques, peri-interventional and post-interventional, will be those that are typically used in each study center.

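### The primary safety endpoint singles out nerve injury, but no visit requires a neurological examination, so milder deficits can be missed and the event-free rate overstated

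*Combined protocol and SAP*

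**What the plan says.** **Endpoint.** Section 5.1 defines the second primary endpoint as "Completion (%) of the ablation procedure without device-related adverse events including in particular nerve injury", with post-procedure and 3 months as its time frame. The Synopsis gives the same definition.

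**Examination content.** Section 6.4.4 states: "Complete physical examination includes, at a minimum, assessments of the skin, lymph nodes, respiratory system, abdomen, cardiovascular system, musculoskeletal system, genitourinary system". Ear/nose/throat completes a list of eight systems, and height and weight are added. There is no neurological item.

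**Timing.** In the visit schedule (Table 3 in 6.4.3, and Table A in the Synopsis), the row "Physical Examination" is marked at baseline, within 24 hours of the procedure, and at 3 months. The row "Adverse Events Assessment" is marked at every visit.

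**What counts as nerve injury.** Section 8.2.3 lists it among the device effects to be assessed with care. It includes thermal injury and puncture of the cord or roots, "potentially resulting in radiculopathy, paresis, and paralysis". The section names no method of assessment.

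**Collection.** Section 6.4.4 says "All device, therapy and/or procedure-related adverse events will be collected for this study from enrollment to the end of the study". Section 8.2.1 is broader: it records events that the investigator observes or the participant reports, whether or not attributed to the device.

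**Eligibility.** Exclusion criterion 17 in 6.3.2 reads "Planned treatment site(s) accompanied by objective evidence of secondary radiculopathy or neurologic compromise".

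**The concern.** The plan names one event as the focus of its primary safety claim, yet the only examination it prescribes does not cover the organ system in which that event occurs. Section 8.2.3 asks for careful assessment without saying how, so a site can follow the protocol to the letter and never test strength, sensation or reflexes.

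Two things are at stake. The first is the direction of the bias: a missed injury counts as a success, and there is no concurrent arm in which the same under-detection would occur. The Synopsis says that results will be set against clinical data from similar devices, and those studies may have looked harder or less hard for nerve injury.

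The second is attribution. The endpoint counts only device-related events. The population has progressive metastatic disease, section 2 describes tumour extension into the spinal canal, and section 7.1 allows cementoplasty after the ablation. Without a recorded baseline finding, even the first question, whether a deficit is new, may go unanswered.

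**Working it through.** **1. The plan's own figures.** The safety endpoint has no figure to reproduce: the Synopsis states a formal hypothesis for pain only. The one computed figure is the sample size in 10.2.
- SD of change = 3 × √(2 × (1 − 0.3)) = 3.55.
- A paired t-test for a 2-point difference at two-sided 0.05 has power 0.908 with n = 36 and 0.899 with n = 35, so 36 is reproduced.
- 36 / 0.70 = 51.4, so 52 is reproduced.

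Adding an examination item changes neither number.

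**2. The schedule against the endpoint.**

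| Visit | Safety endpoint time point | Physical examination | Neurological item required | Adverse-event assessment |
|---|---|---|---|---|
| Baseline | no | yes | no | yes |
| Procedure | no | no | no | yes |
| Within 24 hours | yes | yes | no | yes |
| 1 month | no | no | no | yes |
| 3 months | yes | yes | no | yes |
| 12 months | no | no | no | yes |

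The examinations fall at the right times. What they lack is content.

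**3. Whether other instruments fill the gap.** Section 6.4.4 drops the BPI pain map, which might have shown a new radicular pattern. BPI interference (walking) and EQ-5D-5L (mobility, self-care) pick up functional change but are not neurological tests. Karnofsky is recorded at baseline only.

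**4. Size, as an illustration.** The documents give neither a true nerve-injury rate p nor a detection probability s. I assume p from 2% to 10% and s from 50% to 80%, with n = 52.
- Injured = 52p; recorded = 52ps; reported rate = ps.
- Chance that none is recorded = (1 − ps)^52.

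| p | Injured | Recorded, s = 80% / 50% | Reported rate, s = 80% / 50% | Chance of none recorded, s = 100% / 80% / 50% |
|---|---|---|---|---|
| 2% | 1.0 | 0.8 / 0.5 | 1.6% / 1.0% | 35% / 43% / 59% |
| 5% | 2.6 | 2.1 / 1.3 | 4.0% / 2.5% | 7% / 12% / 27% |
| 10% | 5.2 | 4.2 / 2.6 | 8.0% / 5.0% | 0.4% / 1.3% / 7% |

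Missed injuries = 52p(1 − s). The smallest value is 52 × 0.02 × 0.2 = 0.2 patients and the largest is 52 × 0.10 × 0.5 = 2.6. As a share of 52, the event-free rate is overstated by 0.4 to 5 percentage points. This is an upper bound for the endpoint as a whole, because a patient with another device-related event already counts as a failure.

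**5. Reading a clean result.** With no injury recorded in 52, the exact two-sided 95% upper limit is 1 − 0.025^(1/52) = 6.8%. That limit assumes every injury is detected. If only a fraction s is detected, the limit on the true rate becomes 6.8% / s: 8.6% at s = 80% and 13.7% at s = 50% (from the unrounded 6.85%).

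**The case against.** The strongest reply is that the plan already looks for nerve injury. Section 8.2.3 tells investigators to assess it, 8.2.1 records what the investigator sees as well as what the patient says, and adverse events are assessed at every visit. The examination list is a stated minimum, it includes the musculoskeletal system, and CRF content is not in the documents. Much of this stands. A reader might infer that nerve injury comes to light only if the patient reports it, and these sections do not support that. What remains is that an assessment is asked for but no method is required, so practice may differ across up to ten sites.

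A reader might also infer that the absence of an examination at 1 month is a serious hole. Both endpoint time points have one, so this is minor. It matters only for deficits that resolve before 3 months and for patients lost before then (10.2 expects about 30% attrition).

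Nor is there no baseline at all. Criterion 17 implies some check at entry, so an eligible patient is taken to have no objective deficit at the treatment site. What is missing is a specified method and a recorded finding. Even a recorded normal baseline would not by itself separate device injury from later progression. It shows that a deficit is new, and the examination within 24 hours helps with timing.

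Finally, the rate may be low. Section 2 cites a 50-patient series with no procedure-related complications and a 43-patient study with only minor ones. At p = 2% the bias is about half a patient or less. Zero in 50 is still compatible with a rate up to 1 − 0.025^(1/50) = 7.1%, so the low end of the range is not assured.

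**Conclusion.** The point holds as a gap in ascertainment. The protocol singles out nerve injury in a primary endpoint and requires no neurological examination at any visit. Overt deficits would probably be caught. Milder sensory or motor deficits can be missed, and whether a deficit is new may not be documented. The direction of the bias, towards a better safety rate, follows from the endpoint's definition and needs no assumption.

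The size does rest on assumptions. Over a true rate of 2% to 10% and detection of 50% to 80%, the reported nerve-injury rate is 1% to 8%. No single value in that range can be defended from the documents. Since safety has no hypothesis or threshold, the gap cannot be said to reverse a pass/fail result. It does weaken the comparison with similar devices and the reading of a low or zero count in the postoperative and 3-month reports.

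**What to change.** In 6.4.4, add to the minimum content of the physical examination: *neurological (motor, sensory and reflex findings in the segments related to the treated site)*. Record the findings on the CRF at the three examinations already scheduled: baseline, within 24 hours, and 3 months. Optionally, add a fixed question on new weakness, numbness or sphincter change to the 1-month adverse-event form.

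Keep the endpoint's device-related attribution as it is. Counting every new deficit as a failure unless judged unrelated would be a separate change of endpoint. This gap does not justify it, and in progressive disease it could bias against the device.

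The related-only collection rule in 6.4.4 and the all-events rule in 8.2.1 should be reconciled, since both feed this endpoint.

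Cost: one line of protocol text, a few CRF fields and a few minutes per examination. There is no new visit and no change to 36 or 52. The safety rate may come out less favourable.

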7.3. Concomitant Medication

There are no restrictions to prior or concomitant medications before or during the study. The specific concomitant medications listed below should be documented as concomitant medications and will be updated at each visit:

- Osteoporosis medication(s): antiresorptive medications (e.g., bisphosphonates, parathyroid hormone (PTH), calcitonin), calcium, and vitamin D.
- Steroid(s): any steroid use, including steroid inhalers
- Oral narcotics in the last 24 hours. This information will be converted to oral morphine equivalent dose (OMED) (including transdermal patches)

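### OMED is built from oral narcotics and patches only, so a change of opioid route can put a patient in the wrong 3-month response category in Table 4

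*Combined protocol and SAP*

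**What the plan says.** The rule on opioid input appears twice. Section 6.4.4 (Concomitant pain medications) gives "Oral narcotics in the last 24 hours. This information will be converted to oral morphine equivalent dose (OMED) (including transdermal patches"). Section 7.3 lists "Oral narcotics in the last 24 hours" and continues "This information will be converted to oral morphine equivalent dose (OMED) (including transdermal patches"). Neither section names injected, infused, intrathecal or transmucosal opioids, and no conversion table is given.

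Table 4 in section 6.4.4 (called Table 6-1 in the text above it) then classifies each patient at 3 months from the change in worst pain and the change in OMED. Partial Response can be reached in two ways. The first turns on pain: "Pain reduction of 2 or more on a scale of 0-10 without increase in OMED". The second turns on opioid use, and asks for "OMED reduction of 25% in the last 24 hours or more from baseline without an increase in pain". Complete Response needs a worst pain of 0 and no rise in OMED. Pain Progression can be reached by an OMED rise of at least 25% with pain stable or one point higher. Everything else is Indeterminate. The first two categories count as response and the last two as non-response.

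Two further statements matter. Section 7.3 says "There are no restrictions to prior or concomitant medications before or during the study", so nothing prevents a change of route. Section 6.4.4 says "All over-the-counter, prescription medication and/or herbal supplements used for palliative purposes are recorded on CRFs", so a parenteral opioid given for palliation should be on record even though it does not enter OMED.

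**The concern.** Table 4 is meant to stop a fall in pain from being read as benefit when it was bought with more opioid. It can do this only if OMED measures total opioid use. As defined, OMED measures what is taken by mouth or by patch. A patient who moves from tablets to an infusion shows a fall of up to 100% in recorded OMED, whatever happened to the total.

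What is at stake is the meaning of the 3-month response rate. The trial has one arm and unrestricted analgesia, and the primary endpoint is the unadjusted change in worst pain. Table 4 is the only place where pain and opioid use are read together.

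**Working it through.** **The plan's own figure.** Section 10.2 assumes a 2-point difference, SD 3, correlation 0.3, two-sided alpha 0.05 and power 0.90.

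- SD of the change = √(2 × 3² × (1 − 0.3)) = √12.6 = 3.55.
- Exact paired-t power is 0.899 at n = 35 and 0.908 at n = 36, so 36 completers is reproduced.
- 36 / 0.70 = 51.4, rounded up to 52 enrolled, is reproduced.

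OMED is not an input to any of these, so nothing below changes them.

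**Table 4 applied twice.** I applied the definitions to example patients, first with OMED from oral and patch opioid only (as written), then with OMED from all routes. Readings used: an increase in pain or OMED means any increase; the 25% thresholds mean 25% or more; stable OMED means unchanged. The amounts are illustrative assumptions in OMED units, not figures from the documents and not dosing suggestions.

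*Oral to parenteral.* Baseline: worst pain 7, oral 120, no parenteral. At 3 months: oral 0, with parenteral opioid worth 60, 120 or 180. As written, the OMED change is (0 − 120)/120 = −100% in all three cases. With all routes it is −50%, 0% or +50%.

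| Worst pain at 3 months | As written (all three cases) | All routes, total 60 | All routes, total 120 | All routes, total 180 |
|---|---|---|---|---|
| 7 | PR | PR | Indeterminate | Pain Progression |
| 6 | PR | PR | Indeterminate | Indeterminate |
| 5 | PR | PR | PR | Indeterminate |
| 0 | CR | CR | CR | Indeterminate |
| 8 | Indeterminate | Indeterminate | Indeterminate | Pain Progression |

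The false responses fall into two groups:

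- Pain unchanged or down 1 point: PR is wrong when total opioid use was unchanged or rose.
- Pain down 2 points or more, or to 0: PR or CR is wrong only when total use rose.

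If pain rises, the patient is a non-responder under both versions.

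*Partial switch.* Oral 120 to 90 plus parenteral 90 (total 180), pain 7 to 7: the oral fall is 30/120 = 25%, giving PR as written and Pain Progression with all routes. Oral 120 to 100 plus parenteral 80 (total 180): with pain 7 to 5, PR as written and Indeterminate with all routes; with pain 7 to 7, non-response under both.

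*Parenteral to oral.* Baseline oral 60 plus parenteral 120 (total 180).

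- Oral 180 at 3 months, pain 7 to 7: as written the change is +200%, Pain Progression; with all routes 0%, Indeterminate. Both are non-response.
- Oral 120 at 3 months, pain 7 to 5: as written the change is +100%, Indeterminate; with all routes (120 − 180)/180 = −33%, PR. Here a true response is lost.

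**Size per patient.** 1/36 = 2.8 percentage points for each patient moved between response and non-response.

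**The case against.** The strongest case against the point has four parts.

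*The text does not exclude other routes.* The patch parenthesis shows that a non-oral opioid is converted, and the quantity is a morphine equivalent, which could take any route. Palliative drugs of every kind are "used for palliative purposes are recorded on CRFs". This stands in part: the drug is not lost to the record, and a reader should not infer that other routes are expressly barred. But the text names two sources and stops, so a site or programmer following it would convert only those two.

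*A switch does not by itself give Partial Response.* This stands. The OMED route to PR needs a recorded fall of at least 25% and no more pain. The label is wrong only if total opioid use did not fall enough.

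*The error does not always favour the device.* A reader might infer that it does, because the obvious case is a deteriorating patient who goes onto an infusion. The parenteral-to-oral examples show otherwise. The documents do not say which direction would be commoner.

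*Little depends on it.* The response rate is not among the primary or secondary endpoints in section 5, is absent from the clinical report plan in Table 2, and has no analysis in section 10. This stands and limits the severity. It does not make the rule correct: section 6.4.4 still fixes what will count as treatment response.

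It may also be tempting to read the Karnofsky entry limit of 40 as evidence that many patients will lose the oral route. No section links the two. Attrition of about 30% before 3 months (section 10.2) and withdrawal for progression (section 6.5.2) could remove some of those patients.

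**Conclusion.** The point holds as a minor defect in a stated rule. With OMED taken from oral and patch opioid only, Table 4 can misclassify a patient whose opioid route changes between baseline and 3 months, in either direction. The demonstration rests on a literal reading of sections 6.4.4 and 7.3 and on assumed example amounts.

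The number of patients affected cannot be estimated, because the documents give no frequency of parenteral use or route switching. One could assume that 5%, 10% or 20% of true non-responders switch and apply p + s(1 − p): a true rate of 50% would then read 52.5%, 55% or 60%. That is an upper bound on undocumented shares, since it turns every such switcher into a responder and ignores errors the other way. It should not be taken as an expected bias.

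Nor do the documents support carrying the point to the primary result or to 12 months. The primary endpoint does not use OMED, and response is defined at 3 months only.

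**What to change.** In sections 6.4.4 and 7.3, replace the reference to oral narcotics with all opioids by any route in the last 24 hours. State that they are converted to OMED with one conversion table fixed before analysis, and that Table 4 is applied to that total at baseline and at 3 months.

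This is a cheap improvement: one phrase in two sections and one table. It changes how data are handled, not treatment, visits or sample size. Palliative medication is already recorded, so the main cost is a little more coding. The documents do not describe the CRF fields, so the sponsor should check that dose and route are captured for non-oral opioids.
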